- Purpose of the Study: The purpose of the study is to investigate whether calcium carbonate supplementation during labor can improve uterine contractility and decrease labor dystocia. By conducting this trial, the aim is to provide evidencebased guidance to healthcare providers regarding the potential use of calcium carbonate as a preventive measure for labor dystocia.
- Hypothesis: We hypothesized that pregnant women, those who receive calcium carbonate supplementation will have improve uterine contractility and a shorter labor course.
- Alternative Hypothesis: Calcium supplementation will have no effect on contractility

IV: Study type: Randomized control trial

V: Methods:

Location: Labor and Delivery at Arrowhead Regional Medical Center

- Start: Plan to start at the receipt of IRB approval. We anticipate the duration of the study to be about 2 years.
- Type of research: other
- Inclusion:
- Patients undergoing induction of labor with an intrauterine pressure catheter already in place at the discretion of the OB provider
- Maternal age: >18 years of age
- Gestational age > 37 weeks 0 day
- Cephalic presentation
- Able to understand/read English and/or Spanish
- Exclusion:
 - Maternal age < 18 years of age
 - Incarcerated patients
 - Active labor
 - Active illicit substance use
 - Multiple fetal gestations
 - Bleeding concerning for hemorrhage/placental abruption/placenta previa, or other contraindications to vaginal delivery
 - Aneuploidy or fetal structural anomaly
 - Prior cesarean deliveries
 - Known maternal arrhythmias, hyperparathyroidism, heart failure, kidney failure, liver failure, and history of kidney stones
 - Medications that affect uterine contractility like Magnesium, Terbutaline, Cytotec (need to be 4 hours after administration to enroll)
- Subject recruitment: All women with a term pregnancy, admitted for induction of labor will be asked to participate if age >18 years of age and English/Spanish speaking. We will plan to recruit when a patient is at least 4 cm and greater with an IUPC already in place. Using a baseline Montevideo unit of 200, if we were to aim for a 20% difference with a power of 80%, a sample size of 80 would be the minimum goal to enroll. Therefore, our goal is to enroll at least 40 patients into each group.

Consent:

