 - -Intervention group: Calcium carbonate 500 mg 4 tablets PO x1 -Calcium carbonate (TUMS) is an over-the-counter antacid medication and common side effects include changes in bowel habits like constipation or diarrhea, bloating, gas, and abdominal discomfort. Rare side effects include allergic reactions and hypercalcemia if taken in large amounts. The daily recommended max dose is 8000mg, we will be giving a max of 2000 mg.⁷
- The primary outcome will determine the effect of calcium carbonate on uterine contraction strength, assessed by comparing Montevideo units (MVU), frequency of contractions, and peak of the contractions 30 minutes before medication administration and at 30 minutes interval for a total of 2 hours afterward. To ensure accuracy in MVU measurement, all patients should already have an intrauterine pressure catheter (IUPC) in place at the discretion of the OB provider before they are enrolled. Secondary outcomes include duration of first and second stage of labor, mode of delivery, neonatal outcomes (NICU admission, low APGAR scores), and maternal outcomes (PPH).
- Other maternal information such as height, weight, BMI, age, parity, race, gestational age, cervical dilation/effacement/station at the time of medication administration and after administration, time to delivery, oxytocin use, epidural use, Apgars, perineal laceration, QBL, birthweight, mode of delivery, delivery complications will be obtained to compare among the two groups to make sure there are no confounding factors. Since Pitocin dose is a confounding variable after receiving the medication, patients must be off Pitocin during study period.

- The data collected will be divided into 2 groups: control versus intervention group. Statistical analysis included descriptive statistics to summarize maternal characteristics and clinical outcomes. Normality testing was performed, and appropriate comparative statistical tests were selected, including two-way Student's t-tests, Tukey's tests, or post hoc Student–Newman–Keuls tests as appropriate. A p-value of less than 0.05 was considered statistically significant. Univariate and multivariate linear regression analyses were conducted to identify associations between maternal, fetal, and labor-related variables and study outcomes.
- Uni- and multivariate analysis with linear regression modeling will be used to identify significant associations between maternal, fetal, or labor characteristics.

VII: Risks and Benefits:

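### QBL is already collected, but only PPH, with no cut-off, is named as the blood-loss outcome; naming QBL as a continuous secondary outcome would be more sensitive at no cost

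*Combined protocol and SAP*

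**What the plan says.** In section VI (Study Design and analysis), the sentence on secondary outcomes names duration of the first and second stage, mode of delivery, and then "neonatal outcomes (NICU admission, low APGAR scores), and maternal outcomes (PPH"). PPH is given no volume, time window, measurement method or scale. Yes/no is the natural reading of a diagnosis, but the text does not say so.

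QBL appears in the next bullet, in a list of other maternal information that includes "perineal laceration, QBL, birthweight". The purpose given for that list is: "QBL, birthweight, mode of delivery, delivery complications will be obtained to compare among the two groups to make sure there are no confounding factors". No other use of QBL is stated.

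The analysis paragraph says that "appropriate comparative statistical tests were selected, including two-way" Student's t-tests, Tukey or Student–Newman–Keuls tests, together with linear regression. No method is named for a yes/no outcome. On size, section V states "a sample size of 80 would be the minimum goal to enroll" and "our goal is to enroll at least 40 patients into each group", worked out from Montevideo units alone.

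**The concern.** Two things look out of place.

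- **The role given to QBL.** Blood loss at delivery comes after allocation and after the tablets. A difference in QBL between arms may be an effect of treatment, so it cannot serve as a check that the arms were comparable at the start. If QBL were used as an adjustment variable in a regression for another outcome, part of a treatment effect could be removed.
- **The choice of outcome.** The plan names the category (PPH) and leaves the measurement (QBL) unnamed. Cutting a measured quantity into yes/no loses information, and 40 per arm leaves little to spare. The cut-off is also unset, the control arm receives no medication, and no blinding is described. Nothing in the plan therefore prevents the threshold from being settled after the volumes are known.

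At stake is how informative the trial can be about blood loss. A non-significant PPH count from 80 women could be read as reassurance when it says little.

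**Working it through.** **Inputs from the documents.** 40 per arm; significance at 0.05 ("A p-value of less than 0.05 was considered statistically significant"), taken as two-sided because sidedness is not stated outright. No dropout is given, so none is assumed.

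**Inputs not in the documents (assumptions).** Control PPH rate p from 5% to 50%. A shift in QBL of d = 0.3 to 0.8 SD, with QBL roughly normal after transformation.

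**Step 1: the plan's own figure.** The plan says "Using a baseline Montevideo unit of 200, if we were to aim for a 20% difference with a power of 80" percent, which on a relative reading is 0.20 × 200 = 40 MVU. No SD is given, so N = 80 cannot be reproduced directly. Solving backwards, d = (1.960 + 0.842) × √(2/40) = 0.626, so SD = 40 / 0.626 = 63.9 MVU. Using the t distribution, d = 0.634 and SD = 63.1. This says nothing about blood loss. It only shows that 40 per arm gives 80% power for any continuous outcome that shifts by about 0.63 SD, which is the benchmark used below.

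**Step 2: the same shift read as PPH.** If a share p of controls lies above the cut-off, the treated share is p₁ = 1 − Φ(z − d) for a rise and 1 − Φ(z + d) for a fall, where z = Φ⁻¹(1 − p). Power is the sum, over all pairs of event counts (i, j), of Bin(i; 40, p) × Bin(j; 40, p₁) wherever Fisher's two-sided p < 0.05. With d = 0.634, direct comparison of QBL has 80.0% power. For PPH:

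| Control rate | Rise to | Power | Fall to | Power | Information kept |
|---|---|---|---|---|---|
| 5% | 15.6% | 20.8% | 1.1% | 0.9% | 22% |
| 10% | 25.9% | 36.8% | 2.8% | 8.6% | 34% |
| 20% | 41.8% | 47.1% | 7.0% | 29.1% | 49% |
| 30% | 54.4% | 52.7% | 12.3% | 40.5% | 58% |
| 40% | 64.8% | 54.3% | 18.7% | 46.4% | 62% |
| 50% | 73.7% | 50.7% | 26.3% | 50.7% | 64% |

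**Step 3: information kept by the cut.** The last column is φ(z)² / [p(1 − p)]. At 10%, z = 1.282 and φ(z) = 0.1755, giving 0.0308 / 0.09 = 0.34. At 50%, 0.3989² / 0.25 = 0.64.

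**Step 4: other shifts.** Power for QBL (t-test), against the highest Fisher power for PPH in either direction over the same six rates:

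- 0.3 SD: 26% against 14%
- 0.5 SD: 60% against 36%
- 0.8 SD: 94% against 75%

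QBL is the more sensitive measure in every case tried.

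**Step 5: a check on small counts.** At a control rate of 5%, 40 × 0.05 = 2 events are expected. With no events in one arm, five in the other give p = 0.055 and six give p = 0.026, so even abolishing PPH would rarely reach significance (about 1% of the time).

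**The case against.** The strongest reply is that the list in section VI is loosely written and should not be over-read. Apgars and mode of delivery are on it too, and both are also secondary outcomes, so being on the list does not bar QBL from use as an outcome. The items are to be compared between the groups, and the named methods (t-tests, linear regression) suit QBL. This stands in part: some comparison of QBL is planned. The difference is that Apgar scores and mode of delivery are also named as outcomes, and QBL is not.

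The second reply is that blood loss is peripheral. It is absent from the research question, purpose and hypothesis, and the trial is sized on Montevideo units. The reference list includes a randomised trial of intravenous calcium and blood loss, but the body text does not cite it. This stands, and it limits the weight of the point.

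The third is that 0.63 SD favours QBL because it is simply the shift that gives 80% power. That is fair. At 0.3 SD a QBL comparison would usually be non-significant as well.

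A reader might be tempted to go further in four ways, none of which the documents support:

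- *Most of the power is lost.* More than half of the information is lost only at control rates of about 20% or lower. At 30% to 50% the loss is 36% to 42%. The documents give no rate, and the missing cut-off is what would set it.
- *A real change would almost certainly be missed.* For a rise of 0.63 SD, PPH has 37% power from 10% and 47% from 20%.
- *QBL is discarded.* It is collected and compared between the groups; what it lacks is the status of an outcome.
- *PPH is the only maternal outcome besides mode of delivery.* The durations of the first and second stage are also listed.

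**Conclusion.** The concern holds in limited form. PPH is undefined, and QBL is given the role of a confounder check although it arises after treatment. With 40 per arm, QBL analysed as a continuous measure is more sensitive than yes/no PPH at every assumed rate (5% to 50%) and shift (0.3 to 0.8 SD) examined. The size of the gain is not fixed by the documents. It rests on the assumed PPH rate and shift, on approximate normality of transformed QBL, and on PPH being yes/no and tested by Fisher's test.

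This is a minor improvement to a secondary outcome. The primary MVU conclusion is unaffected, and power for small changes in blood loss stays low at N = 80 on either measure.

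**What to change.** In section VI:

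1. Name QBL in mL as a continuous secondary outcome. Compare arms with an estimate and 95% CI: a ratio of geometric means from the log scale, or a rank-based median difference. State which in advance.
2. Take QBL off the list of items compared to rule out confounding, and state that no analysis adjusts for it.
3. Keep PPH as a descriptive count derived from QBL. Write in the cut-off, time window and measurement method before any outcome data are examined.
4. State that the trial is not powered for blood loss, so the interval rather than the p-value should carry the interpretation.

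The cost is a change of wording. QBL is already on the data list, so no extra data collection or participants are needed.

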- The informed consent process will be conducted by trained research staff and will include all aspects of the study and a full disclosure of the risks, benefits, procedures, and alternatives. The study consent and HIPAA authorization will be signed after all questions have been discussed and answered. Collection of baseline information, including such items as contact information, BP measurements, demographic and pregnancy history information, concomitant medications, and lifestyle information will follow the informed consent process.
- All data will be kept confidential to comply with HIPAA regulations. No
 patient identifiers will be included in the data sets. All data will be kept in a
 password protected folder within the ARMC network and will only be made

- available to study investigators. The database will be controlled, and password-protected.
- All data and records will be kept confidential in accordance with Institutional policies and HIPAA. There will be extremely limited access to subject information. All data will be anonymized before publication. Patient Data Sets will include identifiers that are strictly limited to medical record number, ethnicity, age and sex, along with associated clinical data. Patient Data Sets will be imported into password protected Excel files located in an encrypted folder accessible only to the investigators involved in the study, IRB, and IT on the ARMC server. All published poster presentations, abstracts and papers will be de-identified, with a medical record numbers and any other identifying material removed. Patient's age, parity, sex and race will be used in publication for educational purposes.

VI: Study Design and analysis:

- All patients admitted for term induction of labor will be asked to participate if they
 meet the inclusion criteria as described above. Once consented, the participants
 will be randomly allocated into two groups: control versus intervention group.
 Randomization will be done as block randomization based on maternal BMI at
 time of admission, all odd patients will be enrolled into the control group and all
 even study numbers will be in the intervention group.
 - -Control group: no medication

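### Section VI checks items that arise after allocation, some of them outcomes, between arms for confounding, although calcium may change them and they cannot confound a randomized comparison

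*Combined protocol and SAP*

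**What the plan says.** Section VI lists the data to be collected in one sentence. It starts with maternal characteristics and the cervical exam at the time of the dose. It then moves to the exam after the dose, time to delivery, oxytocin and epidural use, and delivery and newborn results. It ends: "mode of delivery, delivery complications will be obtained to compare among the two groups to make sure there are no confounding factors". No other purpose is given in that sentence.

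Just before it, the same section states: "Secondary outcomes include duration of first and second stage of labor, mode of delivery, neonatal outcomes (NICU admission, low APGAR scores), and maternal outcomes (PPH". The hypotheses in sections II and III expect calcium to improve contractility, shorten labor and reduce cesarean deliveries.

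The regression text appears twice. One statement reads "Univariate and multivariate linear regression analyses were conducted to identify associations between maternal, fetal, and labor-related variables and study outcomes"; the other says "linear regression modeling will be used to identify significant associations between maternal, fetal, or labor characteristics". Neither names covariates, says which model estimates the calcium effect, or limits covariates by timing.

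Allocation is described as random ("Randomization will be done as block randomization based on maternal BMI"), and the comparator is "Control group: no medication".

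**The concern.** A between-arm check for confounding asks whether the groups differed in something other than treatment. That is a sensible question for characteristics fixed before treatment. For a variable that calcium may change, an arm difference can be the treatment effect itself.

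As written, a shorter time to delivery or fewer cesareans in the calcium arm would support the hypotheses in sections II and III, yet would count as a warning of confounding in section VI. A real effect could then be explained away. An analyst who took the sentence at its word could also add such items to a regression of the calcium effect and remove part of that effect.

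**Working it through.** **Step 1. Sort the list by timing and role.**

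| Item | Fixed before the dose? | Outcome role elsewhere in the plan |
|---|---|---|
| Age, height, weight, BMI, race, parity, gestational age, cervical exam at the dose | Yes | None; a balance check is reasonable |
| Mode of delivery | No | Named secondary outcome |
| Apgars | No | Low Apgar is a named secondary outcome |
| QBL | No | Measures the blood loss behind PPH, a named secondary outcome |
| Time to delivery | No | Overlaps first- and second-stage duration, both named secondary outcomes |
| Cervical exam after the dose, perineal laceration, delivery complications | No | None clear |
| Birthweight | Recorded later, but largely fixed before a single dose in labor | None; usable as a descriptor |
| Oxytocin use, epidural use | No time window given | None; co-interventions if they occur after the dose |

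Seven items arise after allocation. Four have two conflicting roles and three have no clear outcome role.

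**Step 2. Inputs for an illustration of size.** Section V gives "Using a baseline Montevideo unit of 200, if we were to aim for a 20% difference with a power of 80" per cent, with 40 patients per group. The effect is 0.20 × 200 = 40 MVU. No SD is stated. With two-sided alpha 0.05 (sidedness assumed), the normal approximation gives

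SD = 40 / [(1.960 + 0.842) × √(2/40)] = 40 / 0.6265 ≈ 63.9.

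The exact t-test gives 63.1. I use 63 and show 50 and 80 as a range.

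**Step 3. Model (assumed).** MVU = 200 + 40 × arm + SD × e. Time to delivery, in SD units, = −r × (MVU − 200)/SD + √(1 − r²) × e₂. Calcium thus changes time to delivery only through MVU (full mediation), and r is the size of the within-arm correlation. The documents give no value for r.

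- Arm shift in time to delivery = r × 40/SD.
- MVU effect after adjusting for it = 40 − (r × SD) × (r × 40/SD) = 40 × (1 − r²), at any SD.

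| r | Shift (SD units, SD 63) | Check significant at p<0.05 | Adjusted MVU effect | Power after adjustment (80% without) |
|---|---|---|---|---|
| 0.2 | 0.127 | 9% | 38.4 | 78% |
| 0.35 | 0.222 | 17% | 35.1 | 74% |
| 0.5 | 0.317 | 29% | 30.0 | 66% |
| 0.7 | 0.444 | 50% | 20.4 | 50% |

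The third column is how often the check would be positive only because treatment works. Power after adjustment is from simulation.

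**Step 4. Sensitivity.**
- SD 50: the check is positive in 11% to 70% of trials; power falls from 94% to between 93% and 67%.
- SD 80: the check is positive in 7% to 34%; power falls from 60% to between 57% and 34%.
- Pre-dose MVU also in the model (pre/post correlation 0.5, SD 63): estimates of about 39, 36, 32 and 23 MVU; power falls from about 90% to 88%, 86%, 81% and 66%.
- Calcium does not shift time to delivery: no attenuation.
- Calcium also shortens time to delivery directly by 0.2 SD: 40 × (1 − r²) − 0.2 × r × SD, or about 36, 31, 24 and 12 MVU at SD 63.
- No calcium effect at all: the adjusted test rejects in about 5% of trials, so there is no false-positive inflation.

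**The case against.** **Outcome roles.** A reader might infer that confounding is the only use planned for all seven items. The documents do not support that. Mode of delivery and low Apgar are named outcomes, QBL measures PPH, and time to delivery largely overlaps the stage durations. An effect on labor duration would be analyzed as a secondary outcome whatever the confounding sentence says. Section VI also plans descriptive statistics for clinical outcomes, which could cover laceration and complications. This narrows the point but leaves the wrong purpose in the text.

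**Adjustment.** A reader might also infer that the plan will adjust the calcium effect for these items. It does not say so: the regressions are described as a search for associations. MVU within two hours of the dose would usually precede delivery, so adjusting it for time to delivery would be an unusual choice. The lack of a covariate rule is, by itself, only missing detail.

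**Pitocin.** The remark "Since Pitocin dose is a confounding variable after receiving the medication" may look like a second instance of the error. The plan deals with Pitocin by design, requiring patients to be off it in the study period, and not by a covariate. It adds little.

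**Predictable allocation.** Odd and even study numbers decide the arm, so selection could cause real baseline imbalance. That supports checking baseline items; it does not turn consequences of treatment into confounders.

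**Size.** The rates in the working show how often an arm difference would be significant, not how often someone would misread it. That step is a judgment.

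**Conclusion.** The point holds as a fault in stated purpose. For seven post-allocation items the confounding check is the wrong purpose. It conflicts with the plan's own hypotheses and secondary outcomes, and no other section repairs it. The exposure is clearest for the post-dose cervical exam, laceration and delivery complications, which have no clear outcome role.

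The primary MVU comparison is not affected as written. Attenuation from 40 to about 38–20 MVU is conditional on an adjustment the plan does not prescribe, on r between 0.2 and 0.7, and on full mediation. Under that mediation and r up to 0.35 it is modest. Confidence is high in the reading of the text and lower in the size of any harm. Severity: minor to moderate.

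**What to change.** 1. Define a time zero for controls that matches the dose time in the calcium arm. Controls receive no medication, so the plan's timing relative to administration has no anchor for them.
2. Limit the balance check to variables fixed before time zero: age, height, weight, BMI, race, parity, gestational age and the cervical exam at time zero. Birthweight may stay as a descriptor.
3. Report the seven post-allocation items by arm as outcomes and delete the confounding purpose for them.
4. Report oxytocin and epidural use by arm as co-interventions, which matters because there is no placebo. Split them into before and after time zero only if times are recorded.
5. Estimate the calcium effect on MVU with a model containing arm, the pre-dose 30-minute MVU and admission BMI, and no variable arising after time zero. Enter BMI as blocked once the blocks are defined, otherwise as continuous.

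The cost is analysis wording and the definition of time zero for controls. Pre-dose MVU and BMI are already collected, and no visits are added. Splitting oxytocin and epidural use would need times that the plan does not say are recorded, so it is optional.

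### Labor duration and mode of delivery have no prespecified treatment effect adjusted for parity and dilation at dosing; the plan relies on a baseline comparison that is weak at 40 per arm

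*Combined protocol and SAP*

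**What the plan says.** All of this is in section VI (Study Design and analysis) unless noted.

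- **Purpose of the baseline items.** Parity and cervical dilation, effacement and station at dosing stand in a list of items that "will be obtained to compare among the two groups to make sure there are no confounding factors". No test, threshold or action is given if the arms differ. The same list contains items that arise after dosing, such as later dilation, time to delivery and mode of delivery.
- **Outcomes affected.** "Secondary outcomes include duration of first and second stage of labor, mode of delivery", with neonatal and maternal outcomes besides. A shorter labor course is part of the hypothesis in section III.
- **Allocation.** "Randomization will be done as block randomization based on maternal BMI". Parity and dilation play no part in it.
- **Arm comparisons.** The tests named are Student's t, Tukey and Student–Newman–Keuls, all unadjusted. The one criterion is general: "A p-value of less than 0.05 was considered statistically significant".
- **Regression.** "Univariate and multivariate linear regression analyses were conducted to identify associations between maternal, fetal, and labor-related variables and study outcomes". No covariate, treatment term or target outcome is named, and only linear regression is offered.
- **Size** (section V, Subject recruitment). "our goal is to enroll at least 40 patients into each group".

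**The concern.** Parity and starting dilation can be expected to bear strongly on how long labor lasts and how it ends. Neither is controlled in the allocation, parity is not restricted at entry, and recruitment begins at 4 cm with no upper limit in that sentence. The arms can therefore differ on both by chance.

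The plan's stated safeguard is to compare the arms and so make sure nothing confounds. In a trial of this size, failing to see a difference is weak evidence that there is none. A moderate imbalance that goes unremarked passes into the unadjusted comparison, and the difference in labor duration or cesarean rate seen in that one trial partly reflects who was in each arm. Even with well-balanced arms, variation that these two variables explain stays in the error term, although both are already recorded.

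**Working it through.** **1. The plan's own figure.** Section V gives "Using a baseline Montevideo unit of 200" and "if we were to aim for a 20% difference with a power of 80%, a sample size of 80 would be the minimum goal". The target is 0.20 × 200 = 40 MVU. No standard deviation is stated, so 80 cannot be reproduced. Solving backwards (two-sided 0.05, normal approximation): SD = 40 × √(40/2) / (1.960 + 0.842) ≈ 63.9 MVU. The size was set on the primary outcome, and nothing below depends on that SD. Only the 40 per arm is used.

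**2. Power of a balance test for a true 20-point parity difference** (n = 40 per arm, two-sided 0.05; the 20 points and the parity levels are assumptions).

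Power = Φ[(0.20 − 1.96 × SE0) / SE1], with SE0 = √(2p̄(1−p̄)/40) and SE1 = √{[p1(1−p1) + p2(1−p2)]/40}.

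- 40% v 60%: SE0 = 0.1118, SE1 = 0.1095; Φ(−0.17) = 43%.
- 30% v 50%: 45%.
- 20% v 40%: 50%.
- 10% v 30%: SE0 = 0.0894, SE1 = 0.0866; Φ(0.285) = 61%.

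Fisher's exact test gives 37% to 53% over the same range. For 80% power, 97 per arm are needed at 40% v 60% and 62 per arm at 10% v 30%.

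**3. An observed split.** 24/40 v 16/40: difference 0.20, SE = √(2 × 0.2462/40) = 0.111, t = 1.80 on 78 df, p = 0.075; Fisher p = 0.117. It passes at 0.05, but narrowly: 24 v 15 gives t-test p = 0.045. At 4/40 v 12/40 the gap would be flagged (chi-square p = 0.025, Fisher p = 0.048).

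**4. How often chance produces a gap of 15 points or more** (6 or more women of 40; exact enumeration of two independent binomials; nulliparous share assumed).

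| Nulliparous | Gap ≥ 15 points | Also t-test p ≥ 0.05 |
|---|---|---|
| 20% | 12% | 7% |
| 30% | 18% | 13% |
| 40% or 60% | 21% | 16% |
| 50% | 22% | 16% |

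A gap of 20 points or more is rarer: 9.3% of trials at 50% nulliparous, and 3.6% also pass the t-test.

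**5. Effect on labor duration in such a trial.** Shift = imbalance × parity gap in hours. With an assumed gap of 3 to 5 hours: 0.15 × 3 = 0.45 hour to 0.15 × 5 = 0.75 hour.

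**6. Value of adjustment for a continuous outcome.** Equivalent unadjusted N = 80/(1 − R²). With an assumed R² of 20% to 30%: 80/0.8 = 100 and 80/0.7 ≈ 114. This formula belongs to the linear model and says nothing about mode of delivery.

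No imbalance figure is given for dilation, because the documents offer no distribution to work from.

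**The case against.** Several counter-arguments have force.

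- **The plan does have a multivariable regression.** Parity is a maternal variable, dilation a labor variable and stage duration a study outcome, so that regression could include them. A reader might infer that the two are collected solely for the balance check; the text does not support that. What stands is that the regression is a search for associations, names no treatment term, and is not presented as the adjusted arm comparison.
- **The check is not blind to a 20-point gap.** Its power is 43% to 61%, and some observed 20-point gaps reach p < 0.05. To say it cannot detect one would be wrong.
- **The text does not call the comparison a significance test**, nor say that non-significance settles the matter. That is inferred from the single p < 0.05 rule. If no criterion applies at all, however, the comparison is no better a basis for ruling out confounding.
- **Chance imbalance is not bias.** Under proper randomization the unadjusted estimate is right on average, and its standard error already allows for such imbalance. This is correct, and it limits the claim to precision and conditional accuracy. The enumeration also assumes simple random allocation, whereas the plan describes odd and even study numbers with BMI-based blocks; whether that is proper randomization is a separate question.
- **A 20-point gap would shift the result more** (0.20 × 3 to 5 hours = 0.6 to 1.0 hour). That shift must not be paired with the 22% and 16% above, which belong to the 15-point threshold.
- **The outcomes are secondary.** Nothing here shows an effect on the contractility outcome or on the sample size.

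**Conclusion.** The concern holds in limited form. For labor-stage duration and mode of delivery, the plan relies on a between-arm comparison of parity and dilation that has only moderate power at 40 per arm, and it specifies no treatment effect adjusted for them. Given an assumed 20% to 60% nulliparous, roughly 7% to 16% of trials would carry a parity gap of 15 points or more that a 0.05 test does not flag. Given an assumed 3 to 5 hour difference for first births, that gap moves the labor-duration result of that trial by 0.45 to 0.75 hour. For labor duration alone, adjustment would be worth about 100 to 114 unadjusted women instead of 80 if R² is 20% to 30%.

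The parity mix, the hours and the R² are assumptions; the documents give none of them. The documents do not support reading this as systematic bias, as a defect in the primary analysis, or as proof that the regression would leave these variables out. It should be changed because the better analysis uses data already being collected.

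**What to change.** Replace the balance-check purpose in section VI with a statement fixed before any outcome data are seen:

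- Arm comparisons of first- and second-stage duration use linear regression, and mode of delivery uses logistic regression or another suitable binary model. Each contains a treatment term, parity (0 v 1 or more) and cervical dilation at time zero, whatever the baseline table shows.
- Time zero is defined in the same way for both arms, because the control group receives no medication and so has no dosing time.
- Nothing measured after dosing enters these models as a covariate. This excludes later dilation, time to delivery and mode of delivery, which stand in the present list.
- Baseline characteristics are tabulated by arm, and significance tests are not used to judge confounding.
- The association-seeking regression, if kept, is labeled exploratory.

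The cost is protocol and SAP wording. Parity and dilation are already collected, and the planned 80 women are unchanged. The one practical addition is recording dilation at the common time zero in the control arm.
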